6.4.4. Missingness Due to COVID-19

For missingness that Covid-19 is identified as the cause by the study team, the following imputation methods will be applied.

- For continuous measures, if missing due to Covid-19,
 - when they are analyzed using ANCOVA for a single timepoint, mLOCF method will be used.
 - when they are analyzed using MMRM with repeated measures, no imputation will be done.
- For categorical variables, if missing due to Covid-19,
 - mLOCF method will be used. This applies to categorical variables that are collected categorically, as well as categorical variables that are derived from measures that are collected as continuous, such as EASI50, EASI75, and EASI 90.
 - for primary and key efficacy measures including IGA 0 or 1 and EASI75, multiple imputation method will be used. Seed = 123456 will be used for multiple imputation. Results from multiple imputations will be aggregated to generate the final estimates for statistical inferences. This will be the main imputation method for these primary and key efficacy measures for visits with missing data due to Covid-19.

All measures collected through ePRO diary device should not be impacted by Covid-19.

For a specific DBL, if Covid-19 is still ongoing at the time of the DBL, the list of visits with missing data due to Covid-19 identified by the study for that lock may not be complete and may

be updated in future locks. The imputation for missingness due to Covid-19 for each DBL is based on the list we receive for that specific lock.

For the lock to occur on 20 May 2020, as there are very limited missing data due to Covid-19, the imputation method specified in this section (Section 6.4.4) will not be applied to this lock.

For the planned locks to occur in February 2021, if the missing data due to Covid-19 does not exceed a prespecified 5% for each of the analysis population set, then there would no special imputation method described in Section 6.4.4 applied.

For the lock in December 2021, there would be no special imputation method described in Section 6.4.4 applied.

6.5. Multicenter Studies

This study will be conducted by multiple investigators at multiple sites internationally. The countries will be categorized into geographic regions, as described in Section 5.2.

6.6. Multiple Comparisons/Multiplicity

As this study is designed to assess the long-term efficacy and safety of baricitinib in patients with AD, no adjustments for multiple comparisons will be utilized in the statistical analyses for this study.

6.7. Patient Disposition

Period 1:

An overview of patient populations will be summarized by treatment group. Frequency counts and percentages of patients excluded prior to randomization by primary reason for exclusion will be provided for patients who failed to meet study entry requirements during screening.

Patient disposition through Weeks 16, 36, and 52 will be summarized using the mITT population. Frequency counts and percentages of patients who complete the study treatment visits or discontinue early from the study along with whether they completed follow-up or did not complete follow-up will be summarized separately by treatment group for patients who are responder mITT, partial responder mITT, and for patients who are nonresponder mITT, along with their reason for study discontinuation. Rescue status for the responder mITT and partial responder mITT population will also be summarized. Frequency counts and percentages of patients who complete the treatment or discontinue treatment early will also be summarized separately by treatment group for patients who are responder mITT, partial responder mITT, and for patients who are nonresponder mITT, along with their reason for treatment discontinuation and their rescue status.

A listing of patient disposition will be provided for the ITT population, with the extent of their participation in the study and the reason for discontinuation. A listing of the ITT population with their treatment assignments for both treatment periods will also be provided.

Period 2:

For Period 2, study and study treatment disposition for Randomized Downtitration Withdrawal Substudy Population will be reported similarly as Period 1 above. Disposition for Period 2 Nonsubstudy Population and Open Label Period 2 Nonsubstudy Population will also be reported.

6.8. Patient Characteristics

Patient characteristics including demographics, baseline characteristics and pre-existing conditions will be summarized descriptively by treatment group. Period 1 summaries will be presented for the responder mITT, partial responder mITT, and nonresponder mITT populations.

Period 2 demographics and baseline characteristics will be presented by each treatment group for Randomized Downtitration Withdrawal Population, for non substudy population, for open label Period 2 non substudy population. No formal statistical comparisons will be made among treatment groups unless otherwise stated.

6.8.1. Demographics

Patient demographics will be based on entry into originating study and summarized as described above. The following demographic information will be included:

- age
- age group (<65 versus ≥ 65)
- age group (<65, ≥ 65 to <75, ≥ 75 to <85, ≥ 85)
- gender (male, female)
- race (American Indian or Alaska Native, Asian, Black or African American, Native Hawaiian or Other Pacific Islander, White, Multiple)
- region (as defined in [Table JAHN.5.1](#))
- country
- weight (kg)
- weight category (<60 kg, ≥ 60 to <100 kg, ≥ 100 kg)
- height (cm)
- BMI (kg/m^2)
- BMI category (<25 kg/m^2 , ≥ 25 to <30 kg/m^2 , ≥ 30 kg/m^2)

A listing of patient demographics will also be provided for the mITT population.

6.8.2. Baseline Disease Characteristics

Baseline disease characteristics will be reported where the baseline is from the originating study. Open-label population uses baseline from JAHN. The following baseline disease information (but not limited to only these) will be categorized and presented for baseline AD clinical characteristics, baseline health outcome measures, and other baseline demographic and disease characteristics as described above:

- duration since AD diagnosis (years)

- duration since AD diagnosis category (0 to <2 years, 2 to <5 years, 5 to <10 years, 10 to <20 years, ≥ 20 years)
- age at diagnosis (years)
- age group at diagnosis (<18 years, ≥ 18 to <50 years, ≥ 50 years)
- validated IGA for AD score
- EASI score
- SCORAD
- body surface area affected by AD
- HADS subscales
- POEM
- Itch NRS
- ADSS Item 2
- DLQI
- Skin Pain NRS
- PGI-S-AD
- prior therapy using originating study baseline (topical therapy only; systemic therapy only; topical and systemic therapy)
- use of cyclosporine prior to entry into originating study (yes, no)
- cyclosporine inadequate response prior to entry into originating study (yes, no)
- cyclosporine intolerance prior to entry into originating study (yes, no)
- cyclosporine contraindication (ineligible) prior to entry into originating study (yes, no)
- cyclosporine inadvisable prior to entry into originating study (yes, no)
- use of TCNI prior to entry into originating study (yes, no)
- TCNI inadequate response prior to entry into originating study (yes, no)
- TCNI intolerance prior to entry into originating study (yes, no)
- TCNI contraindication (ineligible) prior to entry into originating study (yes, no)
- TCNI inadvisable prior to entry into originating study (yes, no)
- vaccine prior to entry into originating study (yes, no)
- originating study baseline renal function status: impaired (estimated glomerular filtration rate [eGFR] <60 mL/min/1.73 m²) or not impaired (eGFR ≥ 60 mL/min/1.73 m²)
- Immunoglobulin E: intrinsic (<200 kU/I) or extrinsic (≥ 200 kU/I)

6.8.3. Historical Illness and Preexisting Conditions

Historical illnesses are described in the originating studies and no additional summaries will be created for Study JAHN.

Preexisting conditions are defined as those conditions recorded in the Preexisting Conditions and Medical History electronic case report form (eCRF), or the Adverse Events eCRF with a start date prior to the first dose of the study drug and stop dates that are at or after the informed consent date or have no stop date (ie, are ongoing). For events occurring on the day of the first dose of study drug, the date and time of the onset of the event will both be used to determine if the event was preexisting. Conditions with a partial or missing start date (or time if needed) will be assumed to be ‘not preexisting’ unless there is evidence, through comparison of partial dates,

to suggest otherwise. Preexisting conditions will be categorized using the Medical Dictionary for Regulatory Activities (MedDRA[®], most current available version) algorithmic standardized MedDRA queries or similar predefined lists of Preferred Terms (PTs) of interest. Frequency counts and percentages of patients with selected preexisting conditions will be summarized by treatment group. Analyses will be presented for the responder mITT, partial responder mITT and nonresponder mITT populations.

6.9. Treatment Compliance

Period 1 patient compliance with study medication will be assessed from Week 0 (Visit 2) to Week 52 (Visit 8) (or Early Termination if it occurs prior to Week 52), using the mITT population. Period 2 compliance will be summarized by treatment group up to Week 16 for the US filing.

All patients are expected to take 3 tablets daily from a blister pack as described in Section 5.2. Each blister pack contains 27 tablets. A patient is considered noncompliant if he or she misses >20% of the prescribed doses during the study, unless the patient's study drug is withheld by the investigator. For patients who had their treatment temporarily interrupted by the investigator, the period of time that dose was withheld will be taken into account in the compliance calculation.

Compliance in the period of interest up to Visit x will be calculated as follows:

$$\text{Compliance} = \frac{\text{total number of tablets dispensed} - \text{total number of tablets returned}}{\text{expected number of total tablets}}$$

where

- total number of tablets dispensed: sum of tablets dispensed in the period of interest prior to Visit x
- total number of tablets returned: sum of the tablets returned in the period of interest prior to and including Visit x
- expected number of tablets: number of days in the period of interest * number of tablets taken per day = $([\text{date of visit} - \text{date of first dose} + 1] - \text{number of days of temporary drug interruption}) * \text{number of tablets taken per day}$.

Descriptive statistics for percent compliance and noncompliance rate will be summarized for the mITT population by treatment group for both study periods. Subintervals of interest, such as compliance between visits, may also be presented. The number of expected doses, tablets dispensed, tablets returned, and percent compliance will be listed for all mITT patient for Week 0 to 52, and Week 52 to 200 for patients entering the randomized downtitration and withdrawal substudies. A listing of overall compliance for the period Week 0 to 200 will also be provided.

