For Weeks 52 to 104, patients enrolled in the substudy will be instructed to take 3 tablets together daily at the same time each day and patients not enrolled in the substudy will be instructed to continue taking 1 tablet daily at the same time each day. The blinded materials provided in the JAHN main protocol will be dispensed to JAHN(7) addendum patients who enter substudy treatment at Week 52. This means that all JAHN(7) addendum patients entered into the substudy will receive 3 tablets daily (see Table JAHN.1). All 3 tablets should be taken together, at the same time each day.

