6.4. Handling of Dropouts or Missing Data

Intercurrent events (ICH E9 R1) are events which occur after randomization such that subsequent data (collected after the intercurrent event) are difficult to interpret.

Depending on the estimand being addressed, different methods will be used to handle missing data as a result of intercurrent events. Intercurrent events can occur through the following:

- application of the censoring rule (including after permanent study drug discontinuation or for responders and partial responders [on Placebo or baricitinib 1-mg] who are rescued to a higher dose [baricitinib 2 mg or baricitinib 4 mg])
- retreatment after downtitration or early withdrawal
- discontinuation
- missing an intermediate visit prior to discontinuation or rescue
- lost to follow-up

Noncensor intercurrent events are events that are not due to the application of any censoring rule (ie, the last 3 items in the list above).

Note that as efficacy and health outcome data can accrue after a patient permanently discontinues study drug or is rescued to either baricitinib 2 mg or baricitinib 4 mg (for responders and partial responders on placebo or baricitinib 1 mg), a censoring rule will be applied to all efficacy and health outcome observations subsequent to these events depending on the estimand being addressed.

The *Period 1 censoring rule* will censor efficacy after permanent study drug discontinuation or for responders and partial responders (on placebo or baricitinib 1 mg) who are rescued to a higher dose (baricitinib 2 mg or baricitinib 4 mg). This censoring rule will be applied to all efficacy endpoints conducted for the responder, partial responder, and nonresponder mITT populations (defined in Section 6.2.1). For responders and partial responders, the censoring rule will censor efficacy data after permanent study drug discontinuation or rescue date, whichever occurs first. For nonresponders, the censoring rule will censor efficacy data after permanent study drug discontinuation.

The *Period 2 censoring rule* will censor efficacy data after permanent study drug discontinuation or after retreatment, whichever occurs first. This censoring rule will be applied to efficacy endpoints and safety conducted for the Period 2 population corresponding to the withdrawal and downtitration substudy.

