6.16. Protocol Deviations

Protocol deviations will be tracked by the clinical team, and their importance will be assessed by key team members during protocol deviation review meetings.

Potential examples of deviations include patients who receive excluded concomitant therapy, significant noncompliance with study medication (<80% of assigned doses taken, failure to take study medication and taking incorrect study medication), patients incorrectly enrolled in the study, and patients whose data are questionable due to significant site quality or compliance issues. Refer to a separate document for the important protocol deviations (IPDs).

The number and percentage of patients having IPD(s) will be summarized within category and subcategory of deviation by treatment group. The summary will be presented for the mITT population. Individual patient listings of IPDs will be provided.

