- Prior use of Cyclosporine (yes, no)
- Reasons Cyclosporine was not used
- Prior use of topical calcineurin inhibitor (TCNI) (yes, no)
- Reasons TCNI was not used

APP.1.2.9.3. Historical Illness and Pre-existing Conditions

Historical illnesses are defined as those conditions recorded in the Pre-existing Conditions and Medical History electronic case report form (eCRF) or from the Prespecified Medical History: Comorbidities eCRF with an end date prior to the informed consent date. The number and percentage of patients with selected historical diagnoses will be summarized by treatment group using the ITT population. Historical diagnoses will be categorized using the Medical Dictionary for Regulatory Activities (MedDRA[®], most current available version) algorithmic standardized MedDRA queries or similar pre-defined lists of preferred terms of interest.

Pre-existing conditions are defined in Section 6.8.3 and will be summarized using the ITT population.

APP.1.2.10. Treatment Compliance

Patient compliance with study medication will be assessed from Week 0 (Visit 2) to Week 104 (Visit 16) or ETV using the ITT population.

All patients are expected to take 1 tablet daily from a bottle for Treatment Period 1 as described in APP.1.2.2. Each bottle contains 36 tablets.

Refer to Section 6.9 for further details on compliance. Analyses will be presented for the ITT population.

APP.1.2.10.1. Background Therapy

Analyses will be presented as described in Section 6.9.1 using the ITT population.

APP.1.2.11. Previous and Concomitant Therapy

Summaries of previous and concomitant medications will be based on the ITT population.

At screening, previous and current AD treatments are recorded for each patient. A summary of previous medications used for AD, including zoster immunization and tuberculosis vaccine and medications that are discontinued after screening and before the first dose of study drug, will be prepared using frequency counts and percentages by preferred medication name, with preferred medication names sorted by frequency. Concomitant therapy will be recorded at each visit and will be classified similarly. An additional summary for previous medications used for AD will be created containing the reason of discontinuation.

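### The compliance denominator runs to the visit date, so time after permanent discontinuation can be counted as noncompliance; the Period 2 tablet count for addendum patients also needs reconciling

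*SAP*

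**What the plan says.** **Denominator.** SAP Section 6.9 divides tablets used (dispensed minus returned) by expected tablets, defined as "number of days in the period of interest * number of tablets taken per day". The days run from first dose to the date of the visit, plus one, and only days of temporary interruption come off. The same section calls a patient noncompliant when more than a fifth of the prescribed doses are missed, and reports the rate by treatment group.

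**Time off drug.** SAP Section 6.4 notes that "efficacy and health outcome data can accrue after a patient permanently discontinues study drug". Footnote a to the protocol's Schedule of Activities (Attachment 1) provides for patients who stay in the study more than 28 days after stopping drug, and lets them combine the early termination visit with follow-up. For exposure, SAP Section 6.14.1 ends the Period 1 count at the earlier of the last dose and the Week 52 date.

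**Tablets per day.** Section 6.9 states: "All patients are expected to take 3 tablets daily from a blister pack as described in Section 5.2". For the open-label addendum, APP.1.2.10 states: "All patients are expected to take 1 tablet daily from a bottle for Treatment Period 1". It sets the span as follows: "Patient compliance with study medication will be assessed from Week 0 (Visit 2) to Week 104 (Visit 16) or ETV using the ITT population". For further detail it refers back to Section 6.9. In Protocol Section 4.6.1, for Weeks 52 to 104, substudy patients take three tablets a day, while "patients not enrolled in the substudy will be instructed to continue taking 1 tablet daily at the same time each day".

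**Deviations.** SAP Section 6.16 lists "significant noncompliance with study medication", meaning under 80% of assigned doses, among possible examples. The team reviews importance, and a separate document governs important deviations.

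**The concern.** Compliance should compare what a patient took with what that patient was meant to take. After a permanent stop nothing more is prescribed, yet the formula keeps adding expected tablets until the visit used. The arithmetic therefore departs from the section's own definition, which rests on prescribed doses. A patient with perfect adherence up to the stop can fall below 80%, and a group with more or earlier discontinuation would show a higher noncompliance rate even if its patients took their tablets equally well.

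The second matter is a gap in specification. APP.1.2.10 gives a tablet count for Period 1 only but carries the assessment into Period 2, where the daily count differs between substudy and nonsubstudy patients. The only other count in the SAP's compliance text is three a day for everyone.

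At stake are the compliance summaries and listings, and possibly some entries in the deviation table.

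**Working it through.** **Inputs.** The formula and the 20% limit come from SAP Section 6.9. Enrolment of 250, 80% completing Week 52, and 30% of those entering the substudy come from Protocol Section 4.8.1. Assumptions: every prescribed tablet is taken up to the stop, all unused tablets are returned, there is no temporary interruption, Period 1 has 364 dosing days, and the Week 52 visit falls on Day 365.

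**The plan's own figure.** 250 × 0.80 = 200 completers; 200 × 0.30 = 60. This matches the roughly 60 substudy patients in Protocol Section 4.4 and APP.1.2.3.1. It leaves 200 − 60 = 140 addendum patients outside the substudy.

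**Permanent discontinuation.** With last dose on Day D and the visit G days later, computed compliance is D/(D + G), because tablets per day cancel. It is below 0.80 when G/(D + G) > 0.20, which is the same as G > 0.25 × D.

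- Visit 28 days after the stop: D/(D + 28) < 0.80 gives D < 112.
- Visit at Day 365: D/365 < 0.80 gives D < 292, about Week 41.7.

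| Stop day D | Visit 28 days later | Visit at Day 365 |
|---|---|---|
| 28 | 50.0% | 7.7% |
| 84 | 75.0% | 23.0% |
| 112 | 80.0% | 30.7% |
| 168 | 85.7% | 46.0% |
| 252 | 90.0% | 69.0% |
| 336 | 92.3% | 92.1% |

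Two further cases: last dose on Day 84 and visit on Day 113 gives 84/113 = 74%; last dose on Day 140 and visit on Day 365 gives 140/365 = 38%. An adherent completer scores 364/365 = 99.7%. If the count ends at the last dose, every row becomes D/D = 100%.

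**Tablet count, addendum.** Assume 364 days each for Weeks 0–52 and 52–104, and tablets taken as Protocol Section 4.6.1 instructs.

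- Outside the substudy, with Section 6.9's three a day applied literally in Period 2: Weeks 52–104 give 364/1092 = 33.3%; Weeks 0–104 give 728/(364 + 1092) = 50.0%. With one a day throughout: 728/728 = 100%.
- In the substudy, 364 + 1092 = 1456 tablets are taken by Week 104. A single multiplier over the whole span fails either way: at one a day, 1456/728 = 200%; at three a day, 1456/2184 = 66.7%. Calculated by period, each is 100%.

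**The case against.** The strongest reply is that the definitions are sound even if the arithmetic is incomplete. Section 6.9 speaks of prescribed doses and Section 6.16 of assigned doses, and neither exists after a permanent stop. That is true, but it is why the formula should follow them: the formula produces the percentage, and its only allowance is for temporary interruption.

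It can also be said that the examples are unfavourable. An early termination visit soon after the last dose does little harm: with an assumed 7-day gap, 84/91 = 92%. The documents give no frequency for long off-drug follow-up. This stands, and it limits the point to patients whose gap is long relative to their time on drug.

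On tablets per day, the three-tablet sentence concerns blister packs, whereas nonsubstudy addendum patients keep receiving bottles after Week 52 (Protocol Section 4.6.3; APP.1.2.2). The formula's multiplier is generic, and Section 6.9 works by period of interest and allows subintervals. A careful programmer could take one a day from the protocol. This largely stands. A reader might infer that the whole group of about 140 would be reported at 33% compliance, or that APP.1.2.10 requires one pooled Week 0–104 ratio. The first arises only if three a day is applied literally, and the second is not stated. What remains is that the SAP leaves the count to be inferred.

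The Visit 2 label for Week 0 changes no number, because the count starts at the first dose. The Week 104 end point in APP.1.2.10, against Week 200 elsewhere in Appendix 1, is likewise a matter for clean-up.

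**Conclusion.** The point holds in limited form. As written, the Section 6.9 formula understates compliance for anyone who stops drug permanently before the visit used. It takes a fully adherent patient below 80% once off-drug time exceeds 20% of the time to that visit (25% of on-drug time). With a 28-day gap this means stops before about Day 112; with a visit at Day 365, stops before about Day 292. Completers are not flagged. Late discontinuers score somewhat low but stay above the limit. These thresholds assume full return of unused tablets and no interruptions. How far a group's rate would move cannot be calculated, because the documents do not say how many patients stay on after stopping or for how long.

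A reader might infer that such patients automatically become protocol deviations. The documents do not support that: the 80% figure is a possible example, importance is reviewed, and the governing document is separate. Nor do they show that this formula is the trial's only measure of adherence, since the main protocol was not supplied. Neither the analysis populations in Section 6.2.1 and Appendix 1 nor the censoring rules in Section 6.4 use compliance, so no efficacy or safety result depends on it.

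The Period 2 tablet count is a smaller, separate gap: an inconsistency to reconcile, not a demonstrated mislabelling.

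**What to change.** In Section 6.9, define expected tablets as (earlier of visit date and last-dose or permanent-discontinuation date − first dose in the period + 1 − days temporarily withheld) × tablets prescribed per day. This adopts the stopping date that Section 6.14.1 already uses for exposure.

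Reconcile Section 6.9, APP.1.2.10 and Protocol Section 4.6.1 on tablets per day in Period 2, and state the agreed multiplier for addendum patients in and outside the substudy. Calculate Periods 1 and 2 separately wherever the daily count changes; build any overall listing from the sum of the two expected counts.

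As clean-up, align the visit label for Week 0 and the end point of addendum compliance with the rest of Appendix 1.

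The cost is a few lines of SAP text and a small programming change. Last-dose dates are already derived, so no new data are needed.
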